4.1.4 Missing data

The study was designed to reduce the risk for missing data as much as possible through the following measures:

- From randomisation to Week 40, the study design allows for one burst and taper of corticosteroid for increased SLE disease activity or non-SLE causes.

- The dose of MMF may be increased up to 3 gm/day in case of suboptimal response.
- Subjects will receive IV methylprednisolone 500 mg on Week 0 (Day 1), prior to receiving the IP.
- Subjects may also receive up to one additional (optional) dose of IV methylprednisolone (≤ 500 mg) for renal or extra-renal disease activity between Week 0 (Day 1) visit and Week 8 visit. This optional dose can be given over two consecutive days.
- Subjects who require additional bursts of OCS will still be allowed to remain in the study, but will be considered non-responders for subsequent responder analyses (such as CRR).

Subjects who discontinue IP will be followed up and asked to come to each visit for the scheduled assessments through the Week 52 visit (or for a minimum of 12 weeks after last dose of IP for subjects for whom IP was discontinued within 12 weeks prior to Week 52).

The following measures will be applied to the second year extension period to also reduce the risk for missing data:

- From Week 52 to Week 92, the study design allows for one burst and taper of corticosteroid.
- Subjects who require additional bursts of OCS during the second year extension period will still be allowed to remain in the study, but may be considered non-responders for subsequent responder analyses (such as CRR at Week 104).

Subjects who discontinue IP in the second year extension period will be followed up until Week 104 (or for a minimum of 12 weeks after last dose of IP for subjects for whom IP was discontinued within 12 weeks prior to Week 104).

Missing safety data will generally not be imputed. However, safety assessment values of the form of $<x$ (i.e. below the lower limit of quantification) or $>x$ (i.e. above the upper limit of quantification) will be imputed as x in the calculation of summary statistics but displayed as $<x$ or $>x$ in the listings.

Details about imputation of partial or missing dates are given in [Appendix D](#). The imputation of single missing items for the derivation of a total score is described in [Appendix E](#).

4.1.4.1 Observed case

A mixed model for repeated measures (MMRM) will be used for all continuous endpoints based on the observed data. MMRM allows the inclusion of repeated effects and the specification of an appropriate variance-covariance structure, which will model any missing data.

4.1.4.2 Last observation carried forward

For secondary and exploratory responder efficacy endpoints, any component with missing value will be imputed using last observation carried forward (LOCF) if only single (non-consecutive) visits are missing data for that component. In the event of two or more consecutive visits with missing data for the same component, the last observed post-baseline value prior to the first missing value will be carried forward only for the first missing value of each sequence, and subjects will be imputed as non-responders for the specific responder endpoint for the second visit on, where data is missing. The responder endpoint is derived based on the imputed values.

If one or more components of SLEDAI 2K and SDI are missing, then the LOCF approach will be used to impute the missing component score. However, if less than 50% of the respective components are available, the data will not be imputed. Additionally, in the event of two or more consecutive visits with missing data for the same component, the last observed post-baseline value prior to the first missing value will be carried forward only for the first missing value of each sequence, and the component score will remain missing for the second visit onwards.

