5.1 Efficacy assessments

Efficacy measurements will be made at the times indicated in the Study Plan (for assessments to be performed at Screening and treatment period, see [Table 2](#) and [Table 4](#), respectively, and for those at Follow-up, see [Table 3](#) and [Table 5](#)).

The efficacy assessments based on laboratory tests include:

- Urine protein to creatinine ratio: This consists of:
 - **24-hour UPCr**: The 24-hour UPCr will be determined on a 24-hour UPCr sample.

This will be performed twice during the screening period, Weeks 0, 12, 24, 36, 52, 64, 76, 88, and 104 and at Early Discontinuation visit.

During the screening period two samples will be required:

- Screening sample at the start of the screening process, after the ICF is signed and
- Stratification sample within 14 days prior to the expected day of randomisation. Without the results of the second (stratification) sample, subjects cannot be randomised. Turn-around time for results from central laboratory is up to 7 days.

Starting from Week 0, the 24-hour UPCR sample must always be collected before the administration of IP. The sample collected at Week 0 (Day 1) will be the baseline sample which must be provided on Day 1 prior to randomisation and administration of first dose of IP.

The collection of the 24-hour UPCR sample should start preferably in the morning of the day before the scheduled visit and end in the morning of the day of the visit. The urine collection can be done within 1 day prior to the visit if the urine sample can be kept refrigerated until the day of the visit. The sample should be kept refrigerated whenever possible. If refrigeration is not possible, subjects should select the coolest possible place to store their urine sample, eg, a cool room or use a portable cooler with ice/ice pack.

In case subject has a medical reason which would impact the validity of the assessment of proteinuria (eg, urinary tract infection, heavy menstruation), or the sample was not collected appropriately, the collection of the sample may be done/repeated as follows:

- Screening samples: As soon as possible before the next scheduled sampling is due
- Week 0: Prior to IP administration (which may require the Visit 1 to be postponed)

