Investigators will not be required, but may continue, to taper OCS dose beyond the target of 7.5 mg/day up to Week 40. Steroid tapering will not be permitted from Week 40 to Week 52.

Steroid “burst and taper”

A steroid burst is defined as one of the following:

Oral corticosteroid increase up to a maximum daily dose of 0.5 mg/kg/day (maximum 40 mg/day) prednisone-equivalent dose for up to a total of 14 days and that must be fully administered and tapered to less than or equal to the pre-burst starting dose by the end of the 14th day. Any course of OCS burst must not extend beyond Week 40 during the first year (starting after Week 0) and Week 92 during the second year extension period (starting after Week 52), regardless of when the course was started.

OR

A maximum of 1 instance of intra-articular, tendon sheath or bursal injections (for a total methylprednisolone \leq 80 mg or equivalent) can be given. Subjects who receive any intra-articular/tendon sheath/bursal injections should not receive OCS burst (and vice versa).

Steroid burst is allowed as follows:

- **From randomisation to Week 40:** One burst and taper of corticosteroids for increased SLE disease activity or for non-SLE activity is allowed.

Subjects who receive more than one steroid “burst and taper” or who violate the above criterion may continue to receive IP after approval by Sponsor/Designee Medical Monitor, but will be considered non-responders for subsequent responder analyses (such as CRR), regardless of whether the OCS “burst” was administered for increased SLE activity or non-SLE causes.

- **Increase in corticosteroids from Week 40 to Week 52:** No increase in OCS, or the use of IV or intra-articular, tendon sheath or bursal injections is allowed from Week 40 until Week 52 assessment.

Corticosteroid dose from Week 52 to Week 100

- If the OCS dose is >7.5 mg/day at Week 52, tapering to ≤ 7.5 mg/day is required by Week 60. Failure to achieve ≤ 7.5 mg/day by Week 60 will lead to discontinuation from IP.
- OCS dose must be tapered to ≤ 5 mg/day at Week 80. OCS tapering below 5 mg/day is allowed at any time until Week 92.
- No change in OCS dose will be allowed from Week 92 to Week 104.
- One burst and taper will be allowed between Week 52 and Week 92.

Increase in corticosteroids for the prevention of adrenal insufficiency

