8.5.2 Analysis of the secondary variable

In addition to the 24-hour UPCR, a composite endpoint will be used to further evaluate the effect of anifrolumab on renal response using the composite endpoint defined in Section 8.4.2, combining response to treatment and lack of restricted therapy. For this analysis, the estimand of interest is the difference in change from baseline in renal response between anifrolumab and placebo, to reflect the effect of the initially assigned and dosed IP (full analysis set). Non-responder imputation is used, ie, subjects treated with restricted treatments beyond protocol-allowed threshold, and those discontinued for other reasons, will be regarded as non-responders. This estimand answers a clinically relevant question comparing the number of subjects able to both tolerate therapy sufficiently to remain on treatment to a given point in time and to achieve adequate response without further medication being required.

The proportion of subjects achieving CRR in the anifrolumab pooled group will be compared to that in the placebo group using a Cochran-Mantel-Haenszel approach (Cochran, 1954) stratified by:

- Results of IFN test at screening using a 4-gene type I IFN diagnostic test (IFN test-high versus. IFN test-low)
- 24-hour UPCR ≤ 3.0 mg/mg versus > 3.0 mg/mg (within 14 days prior to the expected date of randomisation). Without the results of the second (stratification) sample, subjects cannot be randomised. Turn-around time for results from central laboratory is up to 7 days. On rare occasion an extension of 30-day screening window may be allowed if re-collection of the 24-hour UPCR or other required samples is necessary or if the results needed for randomisation are delayed.

Strata with low counts will be collapsed prior to the analysis. Details for collapsing of strata will be pre-specified in the SAP. Further details regarding multiplicity adjustments can be found in Section 8.6.

The estimated treatment effect (ie, the difference in response rate for the pooled anifrolumab group versus the placebo group) and corresponding 95% CI for the difference at Week 52 and

Week 104 will be presented. In addition, the response rate and the corresponding 95% CI within each pooled and treatment group will be presented. The treatment effect at other time points may also be evaluated in a similar way. The individual anifrolumab regimens will also be assessed and presented similarly.

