3.2 Secondary outcome variables

3.2.1 Complete renal response

To evaluate the effect of anifrolumab compared with placebo on renal response in LN subjects, the proportion of subjects achieving CRR at Week 52 will be used. A subject achieves CRR if **all** of the following criteria are met:

- Estimated glomerular filtration rate (eGFR):
 - ≥ 60 mL/min/1.73 m² or no confirmed decrease of eGFR from baseline of $\geq 20\%$
- 24-hour UPCR ≤ 0.7 mg/mg
- No discontinuation of IP or use of restricted medication beyond the protocol-allowed threshold before assessment. Allowed restricted medications are defined in [Appendix A](#) and [Appendix B](#).

The time to achieve CRR will be analysed as supportive analysis and will be derived as the date of first CRR minus the date of first dose of IP. If the subject did not achieve CRR, the time to achieve CRR will be censored at the earliest of the following:

- Date of withdrawal from the study;
- Discontinuation of IP in case of premature discontinuation of IP where the last IP dose is not in the Week 48 analysis visit window;
- Date of the latest of the Week 52 24-hour UPCR and eGFR observations used in analysis (or the date of the latest 24-hour UPCR or eGFR observation before Week 52 if the Week 52 observations are missing) in case of premature discontinuation of IP where the last IP dose is in the Week 48 analysis visit window;
- Date of the Week 104 24-hour UPCR and eGFR observations used in analysis (or the date of the latest 24-hour UPCR or eGFR observation before Week 104 if the Week 104 observations are missing);
- Database extract date.

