4.1.4.3 Non-responder imputation

For the analysis of the secondary and exploratory efficacy responder endpoints (excluding time to modified renal response), subjects will be imputed as non-responders from time at which the criteria are met, in the following cases:

a) Medication criteria

Subjects who meet any of the following medication criteria:

- Subjects who receive any restricted medication (see [Appendix A](#) and [Appendix B](#)) after randomisation or beyond any protocol allowed thresholds will be considered a non-responder from the time the respective medication was administered up to and including Week 104.
- Subjects who meet any of the corticosteroid criteria (see [Appendix B](#)) will be considered a non-responder from the time the condition is met, up to and including Week 24, Week 52, Week 80 or Week 104, depending on the condition and when it is met.
- Subjects who meet any of the MMF criteria (see [Appendix B](#)) will be considered a non-responder from the time the condition is met, up to and including to Week 24, Week 52, Week 80 or Week 104, depending on the condition and when it is met.

b) Discontinued IP

Subjects who prematurely discontinue from IP, including subjects who withdraw from the study. All subjects who have an infusion of IP within the Week 48 analysis visit window will be determined to have completed treatment in the double-blind treatment period.

Non-responder imputation will be applied at all scheduled visits, including missing visits. If a subject does not have a response at a visit, they will be imputed as a non-responder (note that unless IP was discontinued or any of the medication criteria above are met, LOCF will be applied to missing values at the first missed visit in case of consecutive missed visits and the non-responder imputation will be applied to the response values determined after LOCF imputation. See Section 4.1.4.2 for more details on LOCF).

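### Carry-forward of the 24-hour UPCR lets CRR at Week 52 rest on a Week 36 urine, and a second reading of the same SAP rule gives non-response

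*SAP*

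**What the plan says.** - **Endpoint.** SAP Section 3.2.1: "the proportion of subjects achieving CRR at Week 52 will be used". One criterion is a 24-hour UPCR of at most 0.7 mg/mg. CRR is the only secondary endpoint and is Step 2 of the hierarchy in SAP Section 4.1.2.
- **Schedule.** Protocol Section 5.1 plans the 24-hour collection "twice during the screening period, Weeks 0, 12, 24, 36, 52, 64, 76, 88, and 104". Nothing is planned at Weeks 40, 44 or 48. eGFR and spot UPCR are taken at every 4-weekly visit (Protocol Tables 2 and 4).
- **Missing components.** SAP Section 4.1.4.2 says that "any component with missing value will be imputed using last observation carried forward (LOCF", and limits this to cases "if only single (non-consecutive) visits are missing data for that component". In a run of missing visits only the first is filled; from the second on the subject is a non-responder.
- **Order of rules.** SAP Section 4.1.4.3 adds that, unless IP was stopped or a medication criterion was met, "LOCF will be applied to missing values at the first missed visit in case of consecutive missed visits". Non-responder imputation follows that step.
- **Background treatment.** Protocol Section 7.7.3 holds OCS and MMF stable from Week 40 to Week 52. Before that, OCS tapering and MMF decreases are open, and one steroid burst is permitted: "Any course of OCS burst must not extend beyond Week 40 during the first year".

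**The concern.** Allowing one missed visit suits a component measured every 4 weeks, because the carried value is then about 4 weeks old. Applied to the 24-hour UPCR, the same allowance reaches back 16 weeks, and the two longest gaps in the schedule end exactly at the two endpoint visits, Weeks 52 and 104. The SAP sets no maximum age for a carried value.

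Week 36 lies before the stable-dose period that precedes the Week 52 assessment, and Week 88 lies before the corresponding second-year period starting at Week 92. A subject could be counted as a complete responder at the endpoint visit with no 24-hour proteinuria from that visit.

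The rule is also not definite. The SAP does not say what a visit is for a component that is not collected every 4 weeks, so two programmers could derive different CRR results.

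Step 3 of the hierarchy opens only if Step 2 is rejected. The CRR tipping-point analysis in SAP Section 4.2.2 varies only subjects who stopped IP early, so no planned sensitivity analysis varies a carried value.

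**Working it through.** The plan gives no rate or count on this point, so there is no figure to reproduce. Its power statement concerns the primary endpoint and plays no part here.

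**1. Age of the carried value** (scheduled days and windows from SAP Table 2).
- Week 52 minus Week 36: 365 − 253 = 112 days; 112 / 7 = 16 weeks.
- A Week 36 sample anywhere in its window (Days 239 to 266) is (365 − 266) / 7 = 14.1 to (365 − 239) / 7 = 18.0 weeks before Day 365.
- Week 104 minus Week 88: 729 − 617 = 112 days = 16 weeks.
- Gaps between successive planned collections from Week 0: 12, 12, 12, 16, 12, 12, 12, 16 weeks.

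**2. Position against the stable-dose period.** Week 40 is Day 281, and 281 − 253 = 28 days, so Week 36 is 4 weeks before it starts. Week 92 is Day 645, and 645 − 617 = 28 days, so the same holds for Week 88.

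**3. Two readings of the rule.** Take a subject with an observed Week 36 value and no Week 52 value.

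| | Planned 24-hour UPCR assessments counted | Every 4-weekly visit counted |
|---|---|---|
| First missing | Week 52 | Week 40 |
| Week 52 is | first missing, filled from Week 36 | fourth in the run 40, 44, 48, 52 |
| CRR at Week 52 | response if Week 36 UPCR ≤0.7 mg/mg and the other criteria are met | non-response |

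The first reading is the natural one: a sample that was never planned is not missing, and SAP Section 4.2.2 presents CRR only at visits where it can be derived from 24-hour UPCR.

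**4. Who is reached (first reading).** The subject must have met no medication criterion and have a Week 36 value. If Week 36 is missing too, Week 52 is the second missing value and becomes non-response. An unscheduled 24-hour sample in the Week 40 to 48 windows would be carried instead. Stopping IP normally excludes a subject. However, under SAP Section 4.1.3 a subject infused in the Week 48 window who has a Week 52 visit is not imputed for discontinuation at Week 52, and so can be reached.

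**5. Late re-collection.** Protocol Table 2 gives Visit 14 a window of ±7 days, so up to Day 365 + 7 = 372. Protocol Section 5.1 allows re-collection within 2 weeks of the actual visit: 372 + 14 = 386. The SAP Week 52 window closes at Day 378. A permitted sample on Days 379 to 386 falls in the Week 56 window, and Week 52 would be filled from Week 36 although a later real value exists.

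**6. Weight of one subject.** 1/100 = 1 point in the pooled group; 1/50 = 2 points in placebo. The documents give no CRR rates, so the following is illustration only, with assumed rates and an unstratified z-test: p̄ = (x_A + x_P)/150, SE = √[p̄(1 − p̄)(1/100 + 1/50)], z = (x_A/100 − x_P/50)/SE. For 50/100 v 15/50: p̄ = 0.433, SE = 0.0858, z = 0.20/0.0858 = 2.33, p = 0.020.

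| Carried responders recounted as non-responders | p, assumed 50% v 30% | p, assumed 35% v 20% |
|---|---|---|
| none | 0.020 | 0.059 |
| 2 active | 0.035 | 0.097 |
| 5 active | 0.077 | 0.192 |
| 5 active, 2 placebo | 0.024 | 0.063 |

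**The case against.** The best defence is that the case should be rare. Collection for Week 52 opens at Week 50 (Protocol Section 4.2.1), which is Day 351, the first day of the SAP window. A failed sample may be repeated within 2 weeks. Entry to the second year depends on the Week 50 to 52 24-hour UPCR (Protocol Sections 3.9.3 and 4.2.1.1), so a subject doing well has a reason to supply it. A burst lasts at most 14 days and only one is allowed before Week 40, so overlap with the Week 36 sample is unlikely. Many carried responses would also be correct. These points stand for Week 52, but the extension assessment gives no such protection at Week 104.

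SAP Section 4.2.2 already tabulates CRR by spot UPCR beside CRR by 24-hour UPCR at both endpoint visits. That helps, but the table is a summary and does not replace the carried values. Non-responder imputation is itself a single imputation and will misclassify some true responders; that is a cost of the fix.

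A reader might infer that the SAP contradicts Protocol Section 8.5.2, which says "Non-responder imputation is used, ie, subjects treated with restricted treatments beyond protocol-allowed threshold" and extends this to those discontinued for other reasons. It does not. That text covers restricted treatment and discontinuation, and sets no rule for an isolated missing laboratory value in a subject still on IP. Protocol Section 8.5 leaves missing-data sensitivity analyses to the SAP.

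A reader might also infer that the rule favours anifrolumab, or that it inflates CRR by some stated percentage. The documents give no count of missing Week 52 samples, no Week 36 response rate and no evidence of unequal skipping between arms. The larger p-value shifts in the illustration come from recounting active-arm responders only; near-proportional recounting barely changes the result.

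**Conclusion.** The point holds as a defect in the missing-data rule. On its natural reading, SAP Section 4.1.4.2 can credit CRR at Week 52 (or Week 104) on a urine about 16 weeks old, taken before the stable-dose period. On the other reading the same subject is a non-responder.

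The number of subjects is unknown and probably small, and no direction of bias between arms can be shown. The treatment and medication conditions of CRR are still applied up to the endpoint visit without carry-forward; only the proteinuria component is exposed, since eGFR is taken every 4 weeks. The primary endpoint is unaffected, because its mixed model uses observed values. The change is still worth making because CRR is a tested endpoint on which the individual-regimen tests depend.

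This rests on the planned-assessment reading being the one programmed. The detailed medication rules in SAP Appendices A and B were not available to check; they bear on who is excluded, not on how a missing UPCR is filled.

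**What to change.** In SAP Section 4.1.4.2:
- State that 24-hour UPCR is not carried forward to Week 52 or Week 104, and that a subject with no valid 24-hour UPCR for that visit is a non-responder for CRR, aCRR, graded aCRR and PRR.
- State how a permitted re-collection after the analysis window (Day 378 for Week 52) is assigned.
- Keep LOCF for eGFR.

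Report two sensitivity analyses for CRR: the current LOCF rule, with visits defined by planned assessments, and substitution of the same-visit spot UPCR for the missing value. The second can build on the spot-UPCR table already planned in SAP Section 4.2.2.

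The cost is a short SAP amendment and one sensitivity table. The CRR rate may be slightly lower in both arms, and some true responders whose sample was lost will be counted as non-responders; the sensitivities show how much that matters.

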4.1.4.3 Non-responder imputation

For the analysis of the secondary and exploratory efficacy responder endpoints (excluding time to modified renal response), subjects will be imputed as non-responders from time at which the criteria are met, in the following cases:

a) Medication criteria

Subjects who meet any of the following medication criteria:

- Subjects who receive any restricted medication (see [Appendix A](#) and [Appendix B](#)) after randomisation or beyond any protocol allowed thresholds will be considered a non-responder from the time the respective medication was administered up to and including Week 104.
- Subjects who meet any of the corticosteroid criteria (see [Appendix B](#)) will be considered a non-responder from the time the condition is met, up to and including Week 24, Week 52, Week 80 or Week 104, depending on the condition and when it is met.
- Subjects who meet any of the MMF criteria (see [Appendix B](#)) will be considered a non-responder from the time the condition is met, up to and including to Week 24, Week 52, Week 80 or Week 104, depending on the condition and when it is met.

b) Discontinued IP

Subjects who prematurely discontinue from IP, including subjects who withdraw from the study. All subjects who have an infusion of IP within the Week 48 analysis visit window will be determined to have completed treatment in the double-blind treatment period.

Non-responder imputation will be applied at all scheduled visits, including missing visits. If a subject does not have a response at a visit, they will be imputed as a non-responder (note that unless IP was discontinued or any of the medication criteria above are met, LOCF will be applied to missing values at the first missed visit in case of consecutive missed visits and the non-responder imputation will be applied to the response values determined after LOCF imputation. See Section 4.1.4.2 for more details on LOCF).

